5.4 Concomitant Therapies

5.4.1 Concomitant Medication(s)

Concomitant medications must be locally-approved and used at doses and regimens that are considered standard-of-care for the treated indication. Treatment for co-morbidities, disease signs and symptoms and treatment emergent adverse events should be provided as necessary in the judgment of the Investigator. Patients may continue to use any ongoing medications not prohibited by the inclusion/exclusion criteria or treatment plan.

Anti-diarrheals:

- In general Patients should be counseled that diarrhea is a possible side effect of the study treatments and advised to take loperamide or a similar medication as needed if diarrhea develops.
- Glesatinib specific Patients treated with glesatinib may received prophylactic antidiarrheal treatment at the discretion of the Investigator. A regimen recommended for primary prophylaxis for diarrhea is loperamide 2-4 mg beginning with the first dose of glesatinib, followed by 2 mg every 6–8 hours. Loperamide use may be subsequently titrated as needed.

Anti-Emetics: Patients may be premedicated for nausea and vomiting. Recommended anti-emetic agents include granisetron 1 mg as premedication, and then granisetron and/or prochlorperazine as needed.

• Gastric Acid Medications: Proton pump inhibitors and H₂ antagonists should be avoided during treatment on study but are not exclusionary. Switch from use of proton pump inhibitors or H₂ antagonists to use of antacids is preferred. Use of antacids should be avoided 4 hours before and 2 hours after administration of investigational study treatment.

Medications with QTc Prolonging Activity (Sitravatinib and Mocetinostat only): The risk of QTc prolongation in patients receiving the investigational study treatments has not been characterized. Use of medications known to prolong QTc and pose risk of Torsades de Pointes (examples listed in Appendix 3) is to be avoided.

P-450 Considerations, Mocetinostat Specific:

- Warfarin or Coumarin Derivatives Therapeutic doses of warfarin or other coumarin derivative anticoagulants are not permitted in patients treated with mocetinostat. Warfarin has a narrow therapeutic range and mocetinostat can have inhibitory effects on CYP2C9, the main metabolizing enzyme of warfarin. Patients may adopt a different anticoagulant.
- Contraceptives Hormonal contraceptives may be affected by cytochrome P-450 interactions, and are therefore not considered effective for this study, since induction of CYP3A4 may not be excluded in patients receiving mocetinostat.
- Cautioned Medications Caution should be used when mocetinostat is administered to patients taking medications metabolized by CYP2C9, or that inhibit or induce metabolism by CYP2E1 or CYA3A4. See Appendix 3 for examples of medications of interest. If a patient is taking a drug on one these lists, it is encouraged to substitute a different medication if possible.

Herbal Medications/Preparations: Herbal medications and preparations should be avoided throughout the study. Herbal medications include, but are not limited to: St. John's wort, Kava, ephedra (ma huang), gingko biloba, dehydroepiandrosterone (DHEA), yohimbe (yohimbine), saw palmetto, and ginseng.

Transfusions: Patients may receive transfusions as necessary.

Antibiotics: Antibiotics should be used as needed. Patients with neutropenic fever or infection should be treated promptly.

Supportive Care/Palliative Care: Supportive and palliative care for disease related symptoms may be administered at the Investigator's discretion, including the use of analgesics.

Growth Factors: Therapeutic colony-stimulating factors should be used in accordance with ASCO guidelines.

Immunosuppressive Medications: Use of immunosuppressive mediations should be limited to the extent possible to allow testing of the immune-stimulatory mechanisms proposed in this clinical trial. Immunosuppressive medications should be used as needed to manage immune-mediated AEs and the extent required to manage comorbidities and symptoms of disease.

Vaccines: Live attenuated vaccines within 100 days of nivolumab dosing are to be avoided. Inactivated vaccines, such as the injectable influenza vaccine, are permitted.

5.4.2 Concomitant Surgery or Radiation Therapy

The use of surgery to manage cancer lesions during study treatment is discouraged. The impact of the investigation study treatments on wound healing has not yet been characterized. For patients with bone involvement, any foreseeable need for palliative radiotherapy should be addressed before study entry, if possible and clinically appropriate (e.g., bone lesions at risk for spontaneous micro-fractures or painful lesions). However, these treatments may be used in cases where it is medically necessary.

In the event that major surgery is needed during study treatment, the patient should, if possible, interrupt dosing with the assigned investigational study treatment for the duration specified in Table 18.

Table 18: Treatment Interruption for Major Surgery

Drug	Discontinue in Advance	Resume Following
Glesatinib Tablets	1 week	1 week
Sitravatinib Capsules	2 weeks	2 weeks
Mocetinostat Capsules	1 week	1 week

5.4.3 Other Anticancer or Experimental Therapy

Use of approved or investigational anticancer treatment will not be permitted during the study treatment period, including chemotherapy, biological response modifiers, hormone therapies* or immunotherapy. No other investigational drug may be used during treatment on this protocol. Concurrent participation in another therapeutic clinical trial is not allowed.

6 STUDY ASSESSMENTS

6.1 Screening

Voluntary, written, dated, and signed informed consent must be obtained before any study specific procedures are performed. Patients who completed the informed consent process but did not enroll on the study will be considered as screen failures. Limited information will be recorded in the CRF for these patients.

^{*}Certain ongoing hormonal therapies taken to prevent recurrence of a malignancy not under study (e.g., tamoxifen/aromatase inhibitor for breast cancer) may be permitted after discussion with and agreement of the Sponsor's Medical Monitor.

6.2 Study Period

For details on procedures during the study period, see Schedule of Assessments as shown in Table 1.

6.3 End of Treatment Assessment

All patients will be followed for AEs for at least 28 days after the last dose of Study Treatment. See the Schedule of Assessments (Table 1) for evaluations to be performed at the End of Treatment visit.

6.4 Long-Term Follow-up and End of Study Assessment

Survival status and subsequent therapies will be collected during long term follow-up as outlined in the Schedule of Assessments (Table 1) until death or lost to follow-up. Beyond 28 days after last treatment, follow-up may be performed by telephone contact. Treatments received following participation in the study will be collected in the CRF.

6.5 Patient Discontinuation/Withdrawal

Patients may discontinue from study treatment or from study follow-up at any time at their own request, or they may be discontinued at any time at the discretion of the Investigator or Sponsor for safety, behavioral reasons, or the inability of the patient to comply with the protocol required schedule of study visits or procedures at a given study site.

Criteria that may be used to discontinue patients from receipt of study medication will include, but will not be limited to:

- Objective disease progression according to RECIST 1.1 as determined by the Investigator (patients who may derive clinical benefit may continue on treatment at the discretion of the Investigator);
- Global deterioration of health status requiring discontinuation;
- Adverse event;
- Significant protocol violation;
- Lost to follow-up;
- Refusal for further treatment;
- Study termination by Sponsor;
- Death.

Reasons for discontinuation from study follow-up may include:

- Study terminated by Sponsor;
- Lost to follow-up;
- Refusal for further follow-up for survival;
- Death.

If a patient does not return for a scheduled visit, every effort should be made to contact the patient. At least 2 attempts should be made to contact the patient, and each attempt should be recorded in the source documents. In any circumstance, every effort should be made to document patient outcome, if possible. The Investigator should inquire about the reason for withdrawal, request that the patient returns for a final visit, and if applicable, follow-up with the patient regarding any unresolved adverse events.

If the patient withdraws from the study treatment and also withdraws consent for disclosure of future information, no further evaluations should be performed, and no additional data should be collected. The Sponsor may retain and continue to use any data collected before such refusal for further follow-up.

7 PROCEDURES

Every effort should be made to ensure that the protocol required tests and procedures are completed as described. However, it is anticipated that there may be circumstances outside of the control of the Investigator that may make it infeasible to perform a protocol-specified assessment. In these cases, the Investigator will take all steps necessary to ensure the safety and well-being of the patient. When a protocol required test cannot be performed, the Investigator will document in the source document and CRF the reason and any corrective and preventive actions which he/she has taken to ensure that normal processes are adhered to as soon as possible. The study team will be informed of these incidents in a timely fashion.

7.1 Efficacy

All patients enrolled in the study are to be evaluated for disease activity as outlined in the Schedule of Assessments (Table 1). Screening/baseline tumor assessments should include CT or MRI of the chest, abdomen, and pelvis, whole body bone scan, MRI of the brain and evaluation of any superficial lesions. On-study assessments will include all known and suspected sites of disease and will be performed at 8-week intervals until approximately 1-year and then every 16 weeks; bone scans may be performed half as often as other radiology evaluations (i.e., every 16 weeks). The allowable windows for assessments are 4 weeks prior to first study treatment for screening/baseline assessments and ± 10 days for on-study disease assessments. All known and suspected sites of disease

should be evaluated at each assessment. Assessments will be performed until objective disease progression is documented or subsequent anti-cancer therapy is begun.

CT scans should be performed with contrast agents unless contraindicated for medical reasons. If intravenous contrast is medically contraindicated, the imaging modality to be used (either CT without contrast or MRI) should be the modality which best evaluates the disease, and the choice should be determined by the Investigator in conjunction with the local radiologist. Depending on the adequacy for evaluation of disease, a combination of CT without contrast and MRI should most often be used. CT without contrast is preferred for evaluation of lesions in lung parenchyma. MRI is not adequate for evaluation of lung parenchyma but should also be performed to evaluate all other aspects of the chest. MRI of the abdomen and pelvis should substitute for CT with contrast unless the method does not adequately depict the individual's disease, in which case CT without contrast is preferred.

For patients having effusions or ascites, cytological proof of malignancy should be obtained prior to selection of the effusion as a non-target lesion. Effusions that have not been evaluated using cytology or were found to be non-malignant should not be considered to be cancer lesions.

Disease response will be assessed in accordance with RECIST 1.1 (Eisenhauer-2009). Appendix 4 provides guidance in using the response criteria and includes modifications to RECIST 1.1 to address potential temporary treatment effects such as tumor lesion cavitation or flare response. Assessments will be performed until objective disease progression is documented by the Investigator, or subsequent anti-cancer therapy is begun.

Patients experiencing tumor response (Partial Response [PR] or Complete Response [CR]) should undergo confirmatory assessment at least 4 weeks after initial documentation of response. It is acceptable to perform confirmatory assessments at the next appointed evaluation per protocol. Bone scan is required as an element of the confirmation of PR or CR if bone lesions were identified at the baseline assessment.

The Investigator's assessment of disease response and progression will be the basis for patient management and study expansion decision making. Potential exists for individual tumor lesions to cavitate or become otherwise difficult to evaluate for a period of time as the result of beneficial study treatment impact. For example, tumor necrosis and cavitation may result in minor increase in overall individual lesion size or unclear tumor margins prior to recovery to a smaller lesion, development of scar tissue, or complete resolution. For this reason, Investigators may delay reaching the conclusion of disease progression until subsequent on-study disease assessments are performed.

Central radiology review to assess RECIST outcome may be undertaken after Stage 1 of the study. Materials to be forwarded for independent review will be all imaging studies performed at screening and on study, preferably in digital format, using an electronic

transfer through a portal to the review vendor or transfer on compact disc or optical disc. All digital media must be in DICOM format. Films may be forwarded for review if necessary; all films should be originals (second original films acceptable) rather than copies of films.

7.2 Safety Assessments

7.2.1 Adverse Events

Assessment of adverse events will include type, incidence, severity (graded by the National Cancer Institute [NCI] Common Terminology Criteria for Adverse Events [CTCAE, Version 4.03]), timing, seriousness, and relatedness to study treatment.

Signs and symptoms of the patient's cancer diagnosis and/or comorbidities present at baseline will be recorded in the CRF as AEs beginning on Day 1 of study treatment and onward throughout the study. The actual date of onset should be recorded in all cases. Ongoing AEs that change in attribution or severity should have the date of change entered as the "end date" and a new AE record should be opened with the changed details.

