7.2.2 Physical Examination and Vital Signs

A physical examination including all major body systems is mandated at Screening and End of Treatment Visits only. During study treatment, symptom directed physical examinations will be performed.

Vital signs to be assessed include weight, body temperature, blood pressure, and pulse rate. Height will be recorded at screening only. On days were both vital signs and PK sampling are scheduled, the vital signs should be assessed prior to blood sampling.

Clinically significant findings noted during screening will be reflected on the medical history CRF, while those noted during study treatment will be collected on the AE CRFs.

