8.4.1 Adverse Events

8.4.1.1 Treatment-Emergent AEs (TEAEs)

TEAEs are those that first occur or increase in severity after the first dose of study treatment and not more than 28 days after the last dose of study treatment and prior to the initiation of subsequent anti-cancer therapy. Any ongoing TEAE (or any baseline sign/symptom recorded as part of Medical History) that changes in attribution or increases in severity is captured as a new AE.

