9.0 Data Handling

9.1 Missing Dates

9.1.1 Imputation of Partial Adverse Event or Medication Dates

The rules to impute missing start and stop dates will be applied as follows:

Start Date

If the start date is completely missing (i.e., the day, month, and year are all unknown) the start date will not be imputed.

Missing Day Only

- If the month and year of the incomplete date are the same as the month and year of the first dose date, then the day of the first dose date will be assigned to the missing day.
- If either the year is before the year of the first dose date or if years are the same but the month is before the month of the first dose date, then the last day of the month will be assigned to the missing day.
- If either the year is after the year of the first dose date or if both years are the same but the month is after the month of the first dose date, then the first day of the month will be assigned to the missing day.

Missing Month Only

- The day will be treated as also missing and both month and day will be replaced according to the below procedure.

Missing Day and Month

- If the year of the incomplete date is the same as the year of the first dose date, then the day and month of the first dose date will be assigned to the missing fields.
- If the year of the incomplete date is not the same as the year of the first dose date, then January 1 will be assigned to the missing fields.
- If the stop date is complete and the imputed start date is after the stop date, then the start date will be imputed using the stop date.

Stop Date

Missing Day Only

- If the month and year of the incomplete date are the same as the month and year of the last visit date, then the day of the last visit date will be assigned to the missing day.
- If either the year is before the year of the last visit date or if both years are the same but the month is before the month of the last visit date, then the last day of the month will be assigned to the missing day.
- If either the year is after the year of the last visit date or if both years are the same but the month is after the month of the last visit date, then the first day of the month will be assigned to the missing day.

Missing Month Only

- The day will be treated as missing and both month and day will be replaced according to the below procedure.

Missing Day and Month

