11.1.5 Medical History

Medical history will be tabulated using the Safety Population by system organ class (SOC) and preferred term (PT). Medical history will also be listed by patient.

Signs and symptoms of the patient's cancer diagnosis and/or comorbidities present prior to Day 1 of study treatment dosing are recorded in the CRF as medical history.

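### Protocol and SAP disagree on whether baseline symptoms are AEs or medical history, and SAP 9.1.1 can date a documented pre-dose symptom to first dose

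*Protocol*

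**What the plan says.** **Where baseline symptoms are recorded.** Protocol 7.2.1 states that signs and symptoms of the cancer and "comorbidities present at baseline will be recorded in the CRF as AEs beginning on Day 1 of study treatment". It adds: "The actual date of onset should be recorded in all cases". Protocol 7.2.2 then says: "Clinically significant findings noted during screening will be reflected on the medical history CRF". SAP 11.1.5 says that signs, symptoms and comorbidities "present prior to Day 1 of study treatment dosing are recorded in the CRF as medical history".

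**When a new record is opened.** Protocol 7.2.1: "Ongoing AEs that change in attribution or severity should have the date of change entered" as the end date, with a new record for the changed details. That covers a change of grade in either direction. SAP 8.4.1.1 is narrower: an ongoing TEAE, or a baseline symptom held in medical history, "that changes in attribution or increases in severity is captured as a new AE".

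**What counts as treatment-emergent.** Protocol 8.2 counts a pre-existing condition only if it worsens after first dose. SAP 8.4.1.1 requires a first occurrence or a worsening after first dose.

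**Partial onset dates.** SAP 9.1.1, for day and month both missing: "If the year of the incomplete date is the same as the year of the first dose date, then the day and month" of first dose are used. A missing day in the first-dose month is also set to the first-dose day. The section has no exception for events known to be present before dosing.

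SAP 4.1, which lists the changes from the protocol, does not mention any of this.

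**The concern.** The documents put the same information in two places, and the derivation rules give different results depending on which is followed. If baseline symptoms are AE records, they pass through the SAP's partial-date rules and the protocol's record splitting. If they are medical history, they do not.

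The study has no control arm and no randomisation (SAP 6.3), so TEAE percentages will be read at face value. Protocol 1.8.2.1 names fatigue, decreased appetite and cough as non-specific events seen with these agents. They are also plausible baseline complaints in advanced lung cancer, and no within-study comparison would expose an excess from misclassification. SAP 11.1.7.2 counts a patient once per preferred term, so a single misclassified record is enough to make that patient a case.

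**Working it through.** The plan gives no figure to reproduce here. The check compares the rules, then applies SAP 9.1.1 to test dates.

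**1. SAP 9.1.1 applied to a symptom held as an AE.** Example first dose: 15 June 2018.

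| Onset as recorded | Imputed onset | Position |
|---|---|---|
| Complete date before dosing | unchanged | before |
| May 2018 (day missing) | 31 May 2018 | before |
| June 2018 (day missing) | 15 June 2018 | on first dose |
| 2018 only | 15 June 2018 | on first dose |
| 2017 only | 1 January 2017 | before |
| Entirely missing | not imputed | none |

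Only the third and fourth data rows are moved to first dose, and this happens even when the chart shows the symptom at screening. If a complete stop date precedes the imputed start, the stop date is used instead, so an ongoing symptom gets no protection from that rule. SAP 8.4.1.1 counts onsets after first dose and does not say how an onset equal to the first-dose date is flagged. Such a record therefore becomes a TEAE if the flag includes the day of first dose.

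**2. How often a partial date would be moved.** This needs an assumption that is not in the documents: true onset uniform over the L days before dosing, and first dose uniform over a 365-day year.

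*Day missing.* The onset is moved if it falls in the first-dose month. For first dose on day d of the month, the number of such onsets is min(d − 1, L).
- For L of 31 or more, the sum over the year is 7×465 + 4×435 + 378 = 5,373, a mean of 14.72 days. The shares are 14.72/90 = 16%, 14.72/180 = 8% and 14.72/365 = 4%.
- For L = 28, the sum is 7×462 + 4×434 + 378 = 5,348. The share is 5,348/(365×28) = 52%.

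*Day and month missing.* The onset is moved if it falls in the first-dose year. With k days of the year elapsed before first dose (k = 0 to 364), the share is Σ min(k, L)/(365L).
- L = 28: 9,814/10,220 = 96%
- L = 90: 28,755/32,850 = 88%
- L = 180: 49,410/65,700 = 75%
- L = 365: 66,430/133,225 = 50%

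These are shares of partially dated pre-dose onsets only, not shares of patients or of TEAEs.

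**3. Split records.** Take a baseline symptom at grade 2 that falls to grade 1 on treatment. Protocol 7.2.1 closes the first record and opens another dated after first dose. By both definitions this is not a TEAE, because nothing worsened. A flag that looks only at each record's start date would count it. The SAP does not prescribe such a flag, but it has no rule linking a record to its predecessor that would rule one out.

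A change of causality alone is less clear. SAP 8.4.1.1 turns a medical-history symptom into a new AE on that trigger. That is the first AE record for the symptom, it is dated after dosing, and there is no worsening. The section does not say whether it is treatment-emergent.

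**The case against.** The strongest reply is that the definitions are already right. Protocol 8.2 and SAP 8.4.1.1 both require worsening of a pre-existing condition. A reader might infer that the plan counts improving symptoms as TEAEs, but it does not. That would happen only if split records were flagged by date alone, contrary to the stated definition.

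A reader might also infer that partial onsets go to first dose as a rule. They do not: the move is conditional, earlier months and years stay before dosing, and Protocol 7.2.1 asks for the actual onset date.

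Nor is it shown that sites enter baseline symptoms as AEs. Protocol 7.2.2 sends significant screening findings to medical history, SAP 11.1.7.5 repeats that, and the SAP was written against CRF v4.0, which is not available here. If baseline symptoms do sit in medical history, SAP 9.1.1 does not reach them, because it covers only AE and medication dates.

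Finally, imputing toward first dose is a cautious choice for safety data, and counting an ongoing TEAE as related once it is re-judged related is correct.

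Most of this stands and limits the point. It does not remove the conflict between Protocol 7.2.1 and SAP 11.1.5, the different triggers for a new record, or the absence of both from SAP 4.1. Caution justifies imputing to first dose when timing is unknown. It does not justify doing so when the event is documented as present before dosing.

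**Conclusion.** The point holds in limited form. The two documents conflict on where baseline symptoms are recorded and on what opens a new record. Where Protocol 7.2.1 is followed, a stated SAP rule misdates a documented pre-dose symptom whose partial onset matches the first-dose month and year, or for which only the matching year is known. The missing link between split records is a gap that programming could fill wrongly, not an error that the SAP instructs.

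The size in TEAE percentage points cannot be calculated. It would need the baseline prevalence of each symptom, the share of partial dates, the same-day flag convention, and how many affected patients would be counted under that term anyway. None of these is given. The 4% to 52% (day missing) and 50% to 96% (day and month missing) shares above are illustrations that depend on the assumed onset distribution.

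The primary endpoint, ORR, is untouched, and no effect on a decision rule is shown. The consequence is confined to how the single-arm safety tables are read.

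**What to change.** - Reconcile Protocol 7.2.1 and 7.2.2 with SAP 11.1.5 and 8.4.1.1, stating one location for baseline symptoms and one trigger for new records, and list the change in SAP 4.1.
- In SAP 9.1.1, do not impute an onset to first dose when the event is documented, as an AE or in medical history, as present before dosing.
- In SAP 8.4.1.1, flag a continuation record of a pre-existing event as a TEAE only if its grade exceeds the pre-dose grade for the same preferred term in that patient. Records opened only for reduced severity or changed causality inherit the TEAE status of the earlier record. A true TEAE later judged related still appears in the related tables.
- State in the same section how an onset equal to the first-dose date is handled.

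The cost is SAP wording, one derivation and limited review of linked records. SAP 4.0 already provides for a final version before database lock, which is the natural place for the SAP changes.
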